## 7.3 Subject identification

Each subject who signs a consent form for the study will be assigned a unique 9-digit screening number (SNR) in ascending order of recruitment into the study at that center. The first 2 digits will refer to the country, the subsequent 3 digits to the site number, and the following 4 digits will be subject identifiers.

This SNR will be entered into the electronic case record form (eCRF) regardless of whether the subject is actually treated with the study drug (BAY 1163877).

Subjects who are not treated will be considered screening failures. The reason for screening failure should be recorded in the eCRF.

## 8 Treatment(s)

#### 8.1 Treatments to be administered - amended

## Investigational medicinal product (IMP) - test drug

- BAY 1163877 drinking solution (test drug)
- BAY 1163877 tablet (test drug)

Non-investigational product(s) (NIMP)

Not applicable

In study Part 1 / dose escalation + MTD expansion (all comer), twice daily dosing of BAY 1163877 follows the dose-escalation scheme described in Section 6 (Determination of the maximum tolerated dose (MTD)).

Study Part 1 starts with single-dose administration of 50 mg BAY 1163877 on Cycle 1, Day 1. After a "drug-free day" (Cycle 1, Day 2), multiple doses of BAY 1163877 will be given twice daily in an adaptive dose escalation manner, starting at a dose of 100 mg / day (50 mg b.i.d.), with possible dose steps of 100 mg / day. The dose-escalation design proceeds with cohorts of 3 subjects. Cohort expansion, increase or decrease in dose will be decided by the DSMT after consideration of all available safety data of the previous cohort (see Section 6). The dose decision will be guided by model-based dose-response analysis of the DLT rates (see Section 16.4).

In the "tablet bridging cohort", relative bioavailability of the tablet formulation in comparison to the solution formulation will be assessed by administration of a single dose of the tablet formulation on Cycle 1, Day -3 in at least 3 subjects. Starting with Cycle 1, Day 1, subjects enrolled in this cohort will continue with the solution formulation as described above.

In study Part 1 / MTD expansion (all comer), subjects will receive the MTD of

No. BAY 1163877 / 16443

17 Oct 2018 Version 8.0 Page: 56 of 395

BAY 1163877 determined at the end of dose escalation.

For the "food effect assessment", subjects will receive one single dose of BAY 1163877 on Cycle 1, Day -3 immediately (within 5 min) after consumption of a high-fat, high-calorie breakfast, and a second single dose BAY 1163877 on Cycle 1, Day 1 after an overnight fast of at least 8 hours. Further details are provided in Section 8.4.2.2.1.

In study Part 2 / MTD expansion (sqNSCLC + LAC + BC + SCCHN), subjects will be treated with the MTD of BAY 1163877 determined in study Part 1.

In study Part 3 / MTD expansion "Safety cohort" (sqNSCLC + LAC + BC), subjects will be treated with the MTD of BAY 1163877 determined in study Part 1. 

## 8.2 Identity of study treatment

The details of the two formulations of BAY 1163877 planned to be used in this study are given in Table 8-1 (solution) and Table 8-2 (tablet).

Table 8-1: Identity of test drug (IMP): BAY 1163877 solution formulation

Generic name / brand name / INN	Not applicable
Substance code number(s)	BAY 1163877 as BAY 1213802
Material / (formulation)	BAY1163877 HCI H2O SOL 1% 11 mL ORAL
Galenical form / formulation / vehicle and reconstitution, if applicable	Ready-to use solution for oral application
Composition	Active ingredients: BAY 1163877 as hydrochloride
	Other ingredients:
	Hydroxypropylbetadex (solubilizer)
	Sucralose (sweetener)
	Sodium benzoate (preservative)
	Hydrochloric acid (pH-adjustment agent)
	Sodium hydroxide (pH-adjustment agent)
	Purified water (solvent)
Strength (amount of drug per unit) or concentration	1% (10 mg of BAY 1163877 per 1 mL solution)
Type of packaging and content	Amber glass bottle with a withdrawable volume of 11 mL corresponding to 110 mg BAY 1163877
Marketing Authorization Holder if applicable	Not applicable

<sup>47 Part 3 - Safety cohort - was added by Amendment 7, see section 15.6.2.13

No. BAY 1163877 / 16443

17 Oct 2018 Version 8.0 Page: 57 of 395

Table 8-2: Identity of test drug (IMP): BAY 1163877 tablet formulation

Generic name / brand name / INN	Not applicable
Substance code number(s)	BAY 1163877 as BAY 1213802
Material / (formulation)	BAY 1163877 HCL TAB 50.0 mg 363 COAT BAY 1163877 HCL TAB 200.0 mg 364 COAT
Galenical form / formulation / vehicle and reconstitution, if applicable	IR (immediate release) tablets
Composition	Active ingredients: BAY 1163877 as hydrochloride Other ingredients: Cellulose microcrystalline (filler) Lactose monohydrate (filler) Crospovidone (disintegrant) Copovidone (binder) Magnesium stearate (lubricant) Silica colloidal anhydrous (glidant) Lacquer red (coating material)*
	
 
* (contains hypromellose, macrogol, titanium dioxide,ferric oxide red)
 

Strength (amount of drug per unit) or concentration	50 mg BAY 1163877 per tablet 200 mg BAY 1163877 per tablet
Type of packaging and content	HDPE bottles with screw cap closure or blisters of Foil 25/45/60 µm oPA/Al/PP (4320 / 0257) sealed to Foil 20 µm Al sealable to PP (4345 / 0202)
Marketing Authorization Holder if applicable	Not applicable

Labeling: Study medication will be labeled according to the requirements of local law and legislation. Label text will be approved according to the sponsor's agreed procedures, and a copy of the labels will be made available to the study site upon request. Storage conditions are provided on the label.

For all study drugs, a system of numbering in accordance with all requirements of good manufacturing practice (GMP) will be used, ensuring that each dose of study drug can be traced back to the respective bulk ware of the ingredients. Lists linking all numbering levels will be maintained by the sponsor's clinical supplies Quality Assurance (QA) group.

A complete record of batch numbers and expiry dates of all study treatment as well as the labels will be maintained in the sponsor study file.

To reorder clinical drug supplies at least 2 weeks advance notice is required. The site should inform the responsible person for the drug reorder. Contact details of the responsible person are provided on the study team list. The responsible person will notify the site when the order for drug has been placed.

No. BAY 1163877 / 16443

17 Oct 2018 Version 8.0 Page: 58 of 395

All investigational drugs used during the trial will be stored at the site in accordance with instructions given by the clinical supplies delivering department, and will be inaccessible to unauthorized personnel.

Study medication needs to be stored according to the label text. For special storage conditions see investigator site file (ISF) and trial master file (TMF).

In case patients are transferred to a roll-over study (ROS), drug formulation and / or dosage might change compared to this study depending on the course of the clinical development.

## 8.3 Treatment assignment

After completion of the screening examinations, subjects who meet the entry criteria will be placed in the current cohort at the specified dose level. A random list is not necessary because this is a non-randomized open label clinical trial. All subjects will be assigned a unique screening number (SNR), whether or not they are treated after the first signed informed consent. For subject identification, see Section 7.3.

## 8.4 Dosage and administration

Please refer to Sections 8.1 and 8.2 for the dose, route of administration, formulation and duration of treatment.

## 8.4.1 Estimation of safe starting dose

Study Part 1 / dose escalation (all comer)

The first cohort is treated at a starting dose of 100 mg / day of BAY 1163877 (50 mg b.i.d.) which is considered to be safe based on extrapolation from animal toxicological data.

The dose level for each dose-escalation step will be defined primarily based on the results with regard to safety, tolerability, and, if available, PK of the previous dose steps. For this reason, an evaluation will be conducted after each dose step and the decision for the next step will be made by the study team. If necessary, the dose of the next step will be adopted. Details for the dose-escalating steps are given in Section 6 (Determination of the maximum tolerated dose (MTD)).

#### 8.4.2 Selection and timing of dose for each subject - amended

Details for the dose-escalating steps in study Part 1 / dose escalation + MTD expansion cohort (all comer) as well as extent and duration of drug exposure of the individual subject are given in Section 6 (Determination of the maximum tolerated dose (MTD)). Safety monitoring will occur by teleconferences with participation of the investigators and representatives of the sponsor on a regular basis (DSMT). Dose escalation for subsequent cohorts will only be considered after all subjects from the previous cohort have completed the first cycle or early discontinued.

Extent and duration of drug exposure of the individual subject in study Part 2 / dose expansion (sqNSCLC + LAC + BC + SCCHN) and study Part 3 / dose expansion "Safety

No. BAY 1163877 / 16443

17 Oct 2018 Version 8.0 Page: 59 of 395

cohort" (sqNSCLC + LAC + BC) are given in Section 6.48

## 8.4.2.1 Dosing schedule - amended

BAY 1163877 will be given in cycles. Each cycle lasts 21 days. There will be no break between treatment cycles.

Subjects will receive either the solution (IMP 1) or the tablet (IMP 2) formulation of BAY 1163877, except for subjects in the "tablet bridging cohort" who will receive both a single dose using the tablet formulation and multiple doses using the solution formulation.

Study Part 1 / dose escalation + MTD expansion cohort (all comer):

Cycle 1 Day -3 ("tablet bridging cohort" only): Single-dose administration of

BAY 1163877 tablet formulation on Cycle 1, Day -3; thereafter continuation with solution formulation starting on Cycle 1, Day 1 (see dosing schedule

below)

Cycle 1: Single-dose administration of BAY 1163877 on

Cycle 1, Day 1 (in the morning)

No administration of BAY 1163877 on Cycle 1,

Day 2 ("drug-free day")

Twice daily administration of BAY 1163877 on

Days 3-21

Cycle 2 and subsequent cycles: Twice daily administration of BAY 1163877 on

Days 1-21.

Study Part 2 / dose expansion (sqNSCLC + LAC + BC + SCCHN):

- Subjects participating in PK assessments will follow the dosing regimen specified for study Part 1.
- Subjects without PK assessment will receive BAY 1163877 twice daily from Cycle 1, Day 1 ongoing.

Study Part 1 (MTD expansion cohort) or Study Part 2 / "Food Effect Assessment": Approximately 8 subjects will receive single doses of BAY 1163877 on Cycle 1, Day -3 (after consumption of a high-fat, high-calorie breakfast) and on Cycle 1, Day 1 (after an overnight fast of at least 8 hours). BAY 1163877 will not be administered on Cycle 1, Day -2 and Day -1, in the evening of Cycle 1, Day 1 and on Cycle 1, Day 2.

[figure not shown]
Study Part 3 / MTD expansion "Safety cohort" (sqNSCLC + LAC + BC):

• Subjects will receive BAY 1163877 twice daily from Cycle 1, Day 1 ongoing.

-

<sup>48 Part 3 added by Amendment 7, see section 15.6.2.14

<sup>49 Part 3 - Safety cohort - was added by Amendment 7, see section 15.6.2.15

17 Oct 2018 Version 8.0 Page: 60 of 395

Evidence of tumor progression, unacceptable toxicity, consent withdrawal or subject's withdrawal from the study at the discretion of the Investigator may lead to termination of treatment (see Section 7.2.1).

#### **8.4.2.2** Mode of administration

BAY 1163877 will be administered per os (p.o.). Subjects participating in "food effect assessment" will receive a single dose after consumption of high-fat, high-calorie meal (Cycle 1, Day -3) and a single dose after an overnight fast of at least 8 hours (Cycle 1, Day 1) see Section 8.4.2.2.1.

The ready-to-use solution will be administered directly and undiluted via disposable syringe into the mouth of the subject. Immediately after administration, the subject has to drink a glass of water (approximately 200 mL / 7 ounces).

BAY 1163877 tablets should be taken with a glass of water (approximately 200 mL / 7 ounces). Tablets should be swallowed intact and not chewed.

Subjects should not take additional doses of BAY 1163877 to compensate for a missed dose.

#### 8.4.2.2.1 Food effect assessment

To assess the effect of food on the PK of BAY 1163877, a single dose of BAY 1163877 will be administered immediately (within 5 minutes) after consumption of a high-fat, high-calorie breakfast on Cycle 1, Day -3 followed by PK profiling in subjects participating in the MTD expansion cohorts of study Part 1 and Part 2.

Examples of high-fat, high-calorie breakfast:

- A) 50 grams of smoked cooked ham, 30 grams of chicken liver sausage, 50 grams of rye bread, 7 ounces (210 mL) whole milk, 40 grams of butter, 30 grams of butter cheese and 17 Crispbread Wasa Mjölk
- B) 2 eggs (fried), 2 strips of bacon, 2 slices of bread toast, 8 ounces (240 mL) whole milk and 3 teaspoons of butter (for frying and for toast)

High-fat, high-calorie breakfast may be adapted depending on the country while maintaining similar fat and calorie content (approximately 50 % fat and 800 to 1000 calories). Breakfast should be consumed within 25 minutes. No snack is permitted for 4 hours after study drug administration.

BAY 1163877 will not be administered on Cycle 1, Day -2 and Day -1.

A single dose of BAY 1163877 will be administered on Cycle 1, Day 1 after an overnight fast of at least 8 hours (water is allowed *ad libitum*) followed by PK profiling. No food or snack is permitted for 4 hours after drug administration, but water is allowed 1 hour after dosing.

Study drug will not be administered in the evening of Cycle 1, Day 1 and on Cycle 1, Day 2 ("drug-free day").

Starting with Cycle 1, Day 3, BAY 1163877 will be taken twice daily.

No. BAY 1163877 / 16443

17 Oct 2018 Version 8.0 Page: 61 of 395

#### **8.4.2.3** Treatment duration

BAY 1163877 will be administered on a continuous schedule in at least one 21-day Cycle with no break between cycles until progression or as long as clinical benefit is assumed by the investigator or until unacceptable toxicity occurs.

For subjects in the "tablet bridging cohort" and "food effect assessment", treatment starts on Cycle 1, Day -3.

For all other subjects, treatment starts on Cycle 1, Day 1.

Further details on dosing schedule are provided in Section 8.4.2.1.

## 8.4.3 Dose modification and delays - amended

Doses of study drug (BAY 1163877) may be delayed or reduced in case of clinically significant hematologic and other toxicities that are possibly, probably or definitely related to study drug therapy. Toxicities will be graded using the CTCAE v 4.03 (see Section 16.5).

No intra-subject dose escalation will be permitted. However, the dose can be reduced or delayed for an individual subject based on toxicities that are related to study drug.

If a subject experiences a DLT during Cycle 1, the next dose of BAY 1163877 can be delayed for up to 21 days, but only in cases Grade 3 non-hematological toxicities persist no longer than 7 days.

All subjects who are re-treated following a DLT should undergo dose reduction (see Table 8-3).

If the toxicity resolves to  $\leq$  Grade 1, the next dosing of BAY 1163877 at 1 dose level below the current dose (see Table 6-3) can be considered, provided that this dose level has been evaluated during the dose escalation part of the study. Detailed dose adjustments for hematological toxicities are described in Table 8-4. If the subject was dosed at the starting dose level, the subject should be removed from the study. If the toxicity fails to resolve to  $\leq$  Grade 1 within 21 days after the planned treatment date, the subject will be removed from the study. Subjects who experience a Grade 4 non-hematological toxicity will be removed from the study.

## Drug-related adverse events of $\geq$ Grade 3

For ≥ Grade 3 adverse event regarded as related to study drug, the next dosing of BAY 1163877 can be delayed for up to 21 days. If the toxicity fails to resolve to ≤ Grade 1 within 21 days after the scheduled dosing date, the subject will be removed from the study. If the toxicity resolves to ≤ Grade 1, the next dosing of BAY 1163877 at 1 dose level below the current dose (see Table 8-5) can be considered, provided that this dose level has been evaluated during the dose escalation part of the study. Dose adjustments for toxicities are detailed in Table 8-3.

If the re-treatment reproduces the same toxicity grade, the next dosing of BAY 1163877 can be delayed for up to 21 days until the toxicity has resolved to  $\leq$  Grade 1. Re-treatment is possible at 1 dose level below the previous dose.

No. BAY 1163877 / 16443

17 Oct 2018 Version 8.0 Page: 62 of 395

Subjects who experience a Grade 4 non-hematological toxicity will be removed from the study. If more than 2 dose reductions are required, treatment will be permanently discontinued.

Table 8-3: Scheme for dose-level reduction of BAY 1163877 in subjects with solid tumors

Dose level	Action	
-1	1 dose below level of DLT occurrence a	
-2	2 doses below level of DLT occurence a	
-3	Discontinue study drug permanently	

a alternatively, treatment can be continued at an interim dose level with at least 3 subjects evaluated

Table 8-4: Hematological criteria for dose delay and dose modification

Grade a	ANC (10  /L)	Platelets (10  /L)	Dose delay	Dose modification
1 - 2	≥1.0	≥50	Treat as scheduled	No change
3	<1.0 - 0.5	<50 - 25	$Delay^b \ until \leq Grade \ 1$	Decrease 1 dose level c
4	<0.5	<25	$Delay^b \ until \leq Grade \ 1$	Decrease 1 dose level c

- a Applies to all kinds of hematological toxicities; ANC and platelet count displayed as examples.
- b If no recovery after 21 days delay, treatment will be permanently discontinued.
- c Dose will not be re-escalated to original dose level after reduction for toxicity. If more than 2 dose reductions are required, treatment will be discontinued.

Table 8-5: Non-hematological criteria for dose delay and dose modification

Grade	Dose delay	Dose modification
1 – 2	Treat as scheduled	No change
3	Delay b until ≤ Grade 1	Decrease 1 dose level c
4	Discontinue study drug permanently	Discontinue study drug permanently

- a Excludes alopecia. A maximum duration of 48 hours of Grade 3 nausea or vomiting will be allowed and not be considered DLT.
- b If no recovery after 21 days delay, treatment will be permanently discontinued.
- c Dose will not be re-escalated after dose reduction for toxicity. If more than 2 dose reductions are required, treatment will be permanently discontinued.

#### Liver toxicity

Dose modifications of BAY 1163877 for liver toxicity are presented in Table 8-6. Liver toxicity refers to ALT and / or AST and / or bilirubin increases and / or hepatic failure considered possibly related to BAY 1163877, and graded according to CTCAE v4.03.

No. BAY 1163877 / 16443

17 Oct 2018 Version 8.0 Page: 63 of 395

Table 8-6: Dose modifications of BAY 1163877 for liver toxicity - amended

Toxicity	Modification schedule
Grade 1-2	No modifications. Treat as scheduled and check AST, ALT and bilirubin weekly for at least 4 weeks.
Grade 3	Hold BAY 1163877 until recovery to ≤ grade 2 or baseline, then reduce 1 dose level and check AST, ALT and bilirubin weekly for at least 4 weeks. a
- 1 st reappearance	Hold BAY 1163877 until recovery to ≤ grade 2 or baseline, then reduce 1 additional dose level and check AST, ALT and bilirubin weekly for at least 4 weeks a .
- 2 nd reappearance	Withdraw subject from the study treatment.b
Grade 3 with ALT or AST > 8x ULN and a concomitant rise in bilirubin (of any degree compared to previous bilirubin level) or hepatic failure (of any degree)	In case of a negative risk-benefit assessment, consider permanent discontinuation at the first occurrence b,c OR Hold BAY 1163877 until recovery to ≤ grade 2 or
	baseline, then reduce 1 dose level and check AST, ALT and bilirubin weekly for at least 4 weeks a .
-1st reappearance	Withdraw subject from study treatment.b
Grade 4 b	Withdraw subject from study treatment.b

- a Dose will not be re-escalated after dose reduction for toxicity
- b In case of discontinuation, check AST, ALT, and bilirubin weekly until recovery to baseline or stabilization.
- c Subjects with Gilbert's syndrome who develop elevated transaminases should be managed as per the above outlined recommendations for the respective observed elevation of ALT and / or AST.

Patients with AST/ALT > 3xULN with concomitant bilirubin > 2xULN in the absence of another reason for these elevations have to permanently discontinue study drug. Permanent discontinuation also applies to patients with AST/ALT > 8xULN or AST/ALT > 5xULN for > 2 weeks if no other reason is found for these elevations. 50

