## 7.2 Withdrawal of subjects from study

#### 7.2.1 Withdrawal - amended

Subjects will be withdrawn from the study for the following reasons:

- Consent withdrawal
  - At their own request or at the request of their legally acceptable representative
  - At any time during the study and without giving reasons, a subject may decline to participate further. The subject will not suffer any disadvantage as a result.
- Substantial non-compliance with study procedures
  - Subject who is off study drug (BAY 1163877) longer than 8 consecutive days in Cycle 1
  - Subjects lost to follow-up
- Violation of in- / exclusion criteria (subject no longer eligible for the study)
  - If the subject develops conditions which would have prevented his / her entry into the study according to the in- / exclusion criteria, he / she must be withdrawn immediately if safety is concerned; in other cases, the investigator will decide whether there is a conflict with the study objectives.
  - The development of a second malignancy that requires a different treatment.
  - Development of any intercurrent illness or situation which may, in the judgment of the investigator, affect assessments of clinical status and study endpoints to a relevant degree.
  - Subjects with a positive urine beta-HCG test confirming pregnancy. Pregnancy will be reported under the same timelines as a serious adverse event.
- Unacceptable toxicity
  - If, in the investigator's opinion, continuation of study would be harmful to the subject's well-being
  - Severe allergic reactions, such as exfoliate erythrodermia, anaphylaxis, or vascular collapse
  - Any other potential adverse reaction deemed sufficiently serious to warrant discontinuation of treatment by the investigator or his designated associate(s).
  - Use of illicit drugs or other substances that may, in the opinion of the investigator or his designated associate(s), have a reasonable chance of contributing to toxicity

No. BAY 1163877 / 16443

17 Oct 2018 Version 8.0 Page: 54 of 395

or otherwise confound the results.

- Retinal detachment of grade 2 or higher according to CTCAE v4.03 46
- AST/ALT > 3xULN with concomitant bilirubin > 2xULN in the absence of another reason for these elevations
- AST/ALT > 8xULN or AST/ALT > 5xULN for > 2 weeks if no other reason is found for these elevations
- Tumor progression

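### Table 8-6 allows hold-and-reduce for Grade 3 liver toxicity where the paragraph below it and Section 7.2.1 require a permanent stop; its restart grade also differs from the general Grade 3 rule

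*Protocol*

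**What the plan says.** All of this is in the current text of protocol Version 8.0.

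**Table 8-6 (Section 8.4.3, Liver toxicity).** The table covers liver toxicity considered possibly related to BAY 1163877.
- Plain Grade 3 row: "Hold BAY 1163877 until recovery to ≤ grade 2 or baseline, then reduce 1 dose level". A first reappearance leads to a further reduction and a second to withdrawal. The row has no upper limit on ALT or AST.
- A separate row covers "Grade 3 with ALT or AST > 8x ULN and a concomitant rise in bilirubin" of any degree, or hepatic failure. If the benefit-risk assessment is unfavourable, the investigator is to "consider permanent discontinuation at the first occurrence". The alternative, joined by OR, is to hold and then restart one dose level lower.

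**Paragraph below Table 8-6.** Subjects with AST/ALT above 3 x ULN and bilirubin above 2 x ULN, with no other cause, must stop for good. It continues: "Permanent discontinuation also applies to patients with AST/ALT > 8xULN", or above 5 x ULN for more than 2 weeks, again when no other cause is found.

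**Section 7.2.1.** The same criteria appear as reasons for withdrawal under unacceptable toxicity, including "AST/ALT > 8xULN or AST/ALT > 5xULN for > 2 weeks if no other reason is found for these elevations".

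**General rule for related events of Grade 3 or higher (Section 8.4.3).** A subject whose toxicity "fails to resolve to ≤ Grade 1 within 21 days after the scheduled dosing date, the subject will be removed from the study". Table 8-5, for non-hematological Grade 3 events, also requires Grade 1 or lower, and its footnote b adds: "If no recovery after 21 days delay, treatment will be permanently discontinued". Its stated exceptions are alopecia and brief nausea or vomiting. Liver events are not among them.

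**The concern.** An investigator who works from the rows of Table 8-6 may re-expose a subject whose transaminases exceeded 8 x ULN, even with bilirubin rising. An investigator who works from the paragraph below the table, or from Section 7.2.1, must stop the drug unless another cause is found. Two sites can both claim to follow the protocol and treat the same subject in opposite ways, in a situation serious enough for the protocol to have written a mandatory stop.

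The restart grade raises a second, smaller question. A subject whose Grade 3 liver event improves to Grade 2 and stays there is removed under the general rule but restarted one level lower under Table 8-6.

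Safety is a primary objective (Section 4), so consistent handling of drug-related liver injury matters for the subjects and for the safety data.

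**Working it through.** No arithmetic is involved. The check is to apply each text to the same subject. Every case below is Grade 3 and possibly related; cases 1 to 4 have no other cause found.

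| Case | Table 8-6 row | Other current text |
|---|---|---|
| 1. ALT/AST > 8 x ULN with a bilirubin rise | Consider stopping, or hold and restart one level lower | Permanent stop (paragraph below table; 7.2.1) |
| 2. ALT/AST > 8 x ULN, no bilirubin rise or hepatic failure | Plain Grade 3 row: hold, restart one level lower | Permanent stop (same) |
| 3. ALT/AST > 5 x ULN for > 2 weeks | Plain Grade 3 row: keep holding, restart one level lower on recovery | Permanent stop (same) |
| 4. ALT/AST > 3 x ULN with bilirubin > 2 x ULN | Hold, restart one level lower | Permanent stop (same) |
| 5. Improves to Grade 2 and is still Grade 2 at 21 days | Restart one level lower once Grade 2 is reached | Removed (general Grade 3 text; Table 8-5) |

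**Cases 1 to 4.**
- Does Grade 3 extend above 8 x ULN? Yes, on the table's own wording: it has a row for Grade 3 with ALT or AST above 8 x ULN. The plain Grade 3 row therefore also reaches such values when bilirubin does not rise and there is no hepatic failure.
- Can the specific rule be said to override the general one? No. The table and the paragraph sit in the same liver subsection, so both are specific.
- Do the rows carry the no-other-cause condition? No. It stands only in the paragraph and in Section 7.2.1.
- Can the rows be confined to cases with another cause? Only in part. Table 8-6 applies to possibly related events, and Section 9.5.1.2.3 classes an event with a clear alternative explanation as not related. What remains is an event that may be drug-related and also has a contributing cause.
- In case 1, a subject whose bilirubin exceeds 2 x ULN meets two stop criteria at once, because a value above 8 x ULN is also above 3 x ULN.

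The likely origin is visible in the document. The row above 8 x ULN already stands in the Amendment 1 text reproduced in Section 15.1. The footnotes to Sections 7.2.1 and 8.4.3 attribute the withdrawal and liver criteria to Amendment 6. This fits stop rules having been added without a matching change to the rows.

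**Case 5.** The general text and Table 8-5 agree with each other: Grade 1 or lower, within 21 days. Table 8-6 differs on the grade and is silent on the time limit. No sentence states which applies.

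**The case against.** **On the stop criteria.** The texts can be followed together. Permanent discontinuation is one of the options in the row above 8 x ULN, the mandatory paragraph stands directly underneath, and Section 7.2.1 repeats it. An investigator who reads the whole subsection stops when no other cause is found and uses hold-and-reduce otherwise. That reading is not empty: a possibly related event can have a contributing cause, such as liver involvement by the tumor, which eligibility permits. A cautious investigator would probably stop anyway. This stands as the most sensible reading and shows what the fix should say. It does not remove the conflict, because the rows grant the option without the condition and a dose-modification table is likely to be used on its own.

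**On the restart grade.** The opening sentence of the liver subsection sends liver dose modifications to Table 8-6. If Table 8-5 governed liver events, the Table 8-6 threshold would never apply. This largely stands: Table 8-6 most plausibly governs, which is why the point is minor. What is missing is a statement of precedence, including whether the 21-day limit still applies.

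**Stronger readings that the documents do not support.**
- *An open-ended liver hold.* Table 8-6 gives no duration, but silence does not contradict the 21-day limit in the general text. The 2-week criterion also ends many AST/ALT holds, assuming Grade 3 starts above 5 x ULN (the cut-offs are not in the text at hand).
- *A Cycle 1 clash between 8 and 21 days.* Section 7.2.1 withdraws a "Subject who is off study drug (BAY 1163877) longer than 8 consecutive days in Cycle 1", but lists this under non-compliance, and a hold that the protocol directs is not non-compliance. The 21-day delay after a Cycle 1 DLT is itself limited to Grade 3 non-hematological toxicity lasting no more than 7 days.
- *A clash over Ca x PO4.* Section 8.4.4 counts a raised product as a DLT only when it occurs despite phosphate binders. A first episode before binders does not meet that criterion, so resuming the same dose under Table 8-7 does not breach the rule that a DLT leads to dose reduction.

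**Conclusion.** The concern holds in two parts of unequal weight.

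(a) Main part: the Grade 3 rows of Table 8-6 permit hold-and-reduce where the paragraph below them and Section 7.2.1 require a permanent stop. The size of the conflict is the full difference between stopping and re-exposure one dose level lower, for subjects who meet any of the three stop criteria with no other cause found.

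(b) Minor part: the restart grade is Grade 1 in the general rule and Table 8-5, but Grade 2 or baseline in Table 8-6. Table 8-6 is probably meant to govern.

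A reader might infer that the dose-finding result is at risk. It is not: a Cycle 1 event counts as a DLT under Section 8.4.4 because it occurs and is judged related, not because of how the subject is dosed afterwards. DLT counting and the MTD estimate are unchanged. The documents give no rate of Grade 3 liver events, so the number of subjects affected cannot be stated. The change should be made because a mandatory safety stop ought not to sit beside a table that permits the opposite.

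**What to change.** 1. In the Grade 3 rows of Table 8-6, state that hold-and-reduce is allowed only if none of the following is met, or if another reason for the elevation is documented: AST/ALT above 8 x ULN; AST/ALT above 5 x ULN for more than 2 weeks; AST/ALT above 3 x ULN with bilirubin above 2 x ULN. Otherwise the drug is discontinued permanently.
2. Add one sentence to Section 8.4.3: for liver toxicity, Table 8-6 and the paragraph below it replace the general restart grade and Table 8-5, and the 21-day maximum delay still applies.

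Keeping Grade 2 or baseline as the liver restart grade is sensible, because Section 7.1.1.2 admits subjects with liver involvement at ALT/AST up to 5 x ULN.

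The cost is a short wording amendment. A few subjects lose the option of re-treatment. Section 8.4.4 and the MTD analysis need no change.
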